7.4 Reporting Procedures

This study will follow the University of Michigan IRBMED Multi-Site Research Reporting Plan. Please see details in this document in 15.2 Appendix B.

7.5 Follow-up for Adverse Events

Adverse Events will be followed for outcome information until resolution or stabilization. Attempts will be made to collect all relevant information regarding the event in order to properly report the event and determine the appropriate level of follow-up monitoring required. Adverse Events will not be monitored or reported once a participant is off study (e.g. completed their final research study visit [12-month follow-up assessment]).

7.6 Safety Monitoring

Safety monitoring will occur throughout the study as outlined by the Data and Safety Monitoring Plan. At least monthly but more frequently if necessary, the Project Managers will meet with the PIs to review all Risk Reports generated since the last review. These reports will include reports of (1) situations in which increased risk was identified during a study assessment per the guidelines outlined in Section 7.1 “Specifications of Safety Parameters”; (2) any AEs, SAEs, or UPs reported during the study; and (3) any protocol deviations or violations reported during the study. Any patterns of concern or deviations from the risk assessment protocols will be reported to the University of Michigan IRBMED, IMC, or other applicable reporting agency as necessary and outlined under Section 7.4 “Reporting Procedures”, the IMC Charter, or the Data and Safety Monitoring Plan.

An Annual Report will be compiled and will include a list and summary of AEs. In addition, the Annual Report will address (1) whether AE rates are consistent with pre-study assumptions; (2) reason for dropouts from the study; (3) whether all participants met entry criteria; (4) whether continuation of the study is justified on the basis that additional data are needed to accomplish the stated aims of the study; and (5) conditions whereby the study might be terminated prematurely. The Annual Report will be sent to the IRBMED and NCCIH. The IRB and other applicable recipients will review progress of this study on an annual basis. The study team will generate Study Reports for the Independent Monitoring Committee (IMC) using the NCCIH IMC Report Template. Information in the report will include protocol synopsis, enrollment and subject status, demographics and baseline characteristics, safety summary including adverse events, protocol deviations, quality management and outcomes data. Reports will not provide data on primary or secondary endpoints. Study Report tables will be generated only from aggregate (not by group assignment) baseline and aggregate safety data for the study population.

The IRB, IMC, and NCCIH Program Officials will receive copies of all study monitoring, audits, or inspection reports within 30 day of PI receipt.

8. CONDITION DISCONTINUATION

The Independent Monitoring Committee will review and decide on stopping rules for the study. This study will be stopped prior to its completion if: (1) the intervention condition is associated with adverse effects that call into question the safety of the intervention (e.g. there are significant differences [$p < 0.01$] between PPMI and EUC groups in reported levels of AEs or SAEs); (2) difficulty in study recruitment or retention will significantly impact the ability to evaluate the study endpoints; (3) any new information becomes available during the trial that necessitates stopping the trial; or (4) other situations occur that might warrant stopping the trial. Should the trial be stopped prior to its planned completion date for any reason, the PIs will report this stoppage to NCCIH in a reasonable time frame.

Participants may decide to discontinue their participation for any reason, at any time. Any participant requesting to withdraw their participation from the study, either by verbally communicating this information to a research staff member or through written communication (e.g. e-mail, mail, or text message) will no longer be contacted by study staff and their participation in the study will be considered complete. Participant data collected prior to the participant's decision to withdraw from the study will be used in data analyses unless the participant has specifically requested their data be removed. Participants may choose to discontinue participation in the intervention portion of the study (e.g. PPMI or EUC sessions) and will remain active in the study and continued to be followed with their permission. Research staff may choose to end any assessment or condition session early, using clinical discretion, if (1) they believe it is in the best interest of the participant (e.g. the participant becomes upset and/or is unable to continue, medical emergency, etc.), or (2) if staff believe their safety is at risk. As noted above, individual study participation may also be ended by PIs discretion. Reasons for involuntary study withdrawal will be included in the informed consent document and may include: (1) if it is not in the best interest or is harmful to the participant to stay in the study; (2) if the researcher believes the individual's participation is harmful to others or staff; (3) the participant becomes ineligible to participate (e.g. no longer can provide voluntary consent, changes in competency, etc); (4) the participant does not follow instructions from the researchers (e.g. does not complete any of the study sessions or is determined to be "lost to follow-up"); (5) the study is suspended or canceled; or (6) other administrative reasons or unanticipated circumstances.

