7. SAFETY ASSESSMENTS

Once a participant has been enrolled in the study, their safety will be monitored throughout their duration on study in a variety of ways. As lead PIs, Drs. [name] and [name] will have the ultimate responsibility for monitoring the overall safety of the participants in the study, determining whether an event is considered an adverse event (AE) or serious adverse event (SAE), and reporting events as needed to the appropriate committees and agencies. Local site study personnel will be expected to notify the lead PIs, Project Managers, or other designated coordinating center personnel of serious

adverse events, noncompliance, or other study related problems as soon as they are identified. In all instances where participant safety is a concern, the participant will be evaluated and connected with the appropriate level of treatment services necessary. Senior clinicians are always on call for consultation if a participant seems distressed or needs special attention. All participants are instructed on how to obtain emergency care, should that be required. As a requirement of the NCCIH, this study will also include an Independent Monitoring Committee (IMC) or other study monitor which may perform oversight functions and report their observations and findings to the IRB or designated official as needed. Functions could include: observing recruitment and enrollment procedures and the consent process for individuals, overseeing study interventions and interactions, reviewing monitoring plans, or overseeing data matching, data collection, and analysis. These monitors may discuss the research protocol with the investigators, interview human subjects, and consult with others outside of the study about the research. The IMC or any other monitoring entity will have authority to stop a research protocol in progress, remove individual subjects from a research protocol, and take whatever steps are necessary to protect the safety and well-being of human subjects. Any patient safety events will be documented and reported to the appropriate entities (e.g. IRB, NCCIH, IMC, etc.) based on the study reporting requirements outlined below (see Section 7.4 “Reporting Requirements”) and the Data and Safety Monitoring Plan (DSMP) for this study.

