9.4 Interim Analyses and Stopping Rules

There are no formal interim analyses planned for this RCT. Recommendations of the Independent Monitoring Committee, IRB, the sponsor(s), or relevant local regulatory authorities, which may include review of serious, unexpected, and related AEs may result in suspension of further study conditions at a site. The study sponsor(s) retain the authority to suspend additional enrollment and study conditions for the entire study, as applicable. Findings that might trigger a safety review are the number of overall SAEs, the number of occurrences of a particular type of SAE, severe AEs/reactions, or increased frequency of events.

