10.3.5 Monitoring

Data quality and protocol compliance will be monitored throughout the study in a variety of ways. A full schedule for reviews will be included in the Manual of Procedures (MOP) but will be outlined here. Review of the rate of subject accrual and compliance with inclusion/exclusion criteria will occur monthly during the recruitment phase to ensure that a sufficient number of participants are being enrolled, in keeping with proposed recruitment projections, and that they meet eligibility criteria and fulfill the targeted ethnic diversity goals outlined in the grant proposal (Targeted/Planned Enrollment Table). Accrual reports will be submitted to NCCIH at least every 4 months and included in the IMC annual reports. Data on adherence to the condition protocol will be collected on an ongoing basis during the conduction of the study by research staff and reviewed monthly by the PI/Project Managers. Adherence of participants will be evaluated by the Project Manager. If adherence falls below the expected rate, which might inhibit the ability of the study to test its primary hypotheses, the Project Managers will suggest a conference call for study investigators to discuss methods for improving adherence. Study progress and safety will be reviewed monthly (and more frequently if needed). Progress reports, including patient recruitment, retention/attrition, and AEs will be provided to the Independent Monitoring Committee annually. An Annual Report will be compiled and will include a list and summary of AEs. In addition, the Annual Report will address (1) whether AE rates are consistent with pre-study assumptions; (2) reason for dropouts from the study; (3) whether all participants met entry criteria; (4) whether continuation of the study is justified on the basis that additional data are needed to accomplish the stated aims of the study; and (5) conditions whereby the study might be terminated prematurely. The Annual Report will be sent to the Independent Monitoring Committee and will be forwarded to the IRB and NCCIH. The IRB and other applicable recipients will review progress of this study on an annual basis.

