The study team will generate Study Reports for the Independent Monitoring Committee using the NCCIH IMC Report Template. Information in the report will include protocol synopsis, enrollment and subject status, demographics and baseline characteristics, safety summary including adverse events, protocol deviations, quality management and outcomes data. Reports will not provide data on primary or secondary endpoints. Study Report tables will be generated only from aggregate (not by group assignment) baseline and aggregate safety data for the study population.

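### The one numerical illustration of a safety stop, a PPMI-versus-EUC difference in AEs or SAEs at p<0.01, cannot be evaluated from the pooled Study Report tables, and no supplied section assigns an arm comparison

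*Combined protocol and SAP*

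**What the plan says.** Section 8 (Condition Discontinuation) leaves the stopping rules to the Independent Monitoring Committee and lists four grounds for ending the trial early. The first is that the intervention is "associated with adverse effects that call into question the safety of the intervention (e.g. there are significant differences" at p<0.01 "between PPMI and EUC groups in reported levels of AEs or SAEs"). The test, its sidedness and the unit of count (participants or events) are not given.

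Section 7.6 (Safety Monitoring) describes what the committee is sent: "Study Report tables will be generated only from aggregate (not by group assignment"). Section 12 (Committees) repeats it: "Study Report tables will be generated only from aggregate (not by group assignment) baseline and aggregate safety data for the study population".

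The other safety triggers carry no number and no contrast between arms. Section 9.4 says: "Findings that might trigger a safety review are the number of overall SAEs", and goes on to types, severity and frequency of events. Section 11.4 repeats this list. Section 12 adds an unquantified example about injuries or illnesses attributable to participation. Section 9.4 plans no formal interim analysis.

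The Annual Report is described twice. Section 7.6 says: "The Annual Report will be sent to the IRBMED and NCCIH". Section 10.3.5 says: "The Annual Report will be sent to the Independent Monitoring Committee and will be forwarded to the IRB and NCCIH". Neither says whether its list of AEs is pooled.

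**The concern.** A between-arm p-value needs counts by arm, and the tables prepared for the body that decides on stopping have no arms. This is a mismatch between two statements in the plan, not merely a missing detail.

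If the committee works only from those tables, it cannot tell an imbalance that meets the protocol's own illustration from an even split, and nothing in a pooled table would prompt it to ask. What could be missed is a difference in the frequency of events that do not reach the committee one by one. Section 7 lists overdose-risk situations, suicidal ideation and hospitalization for mental health or substance use among the events expected in this population. For events with a high background rate, comparing arms is the natural way to separate an intervention effect from background.

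**Working it through.** **Inputs.** Threshold p<0.01, PPMI versus EUC (Section 8). Arms of 100 (Section 9.2). Pooled tables (Sections 7.6 and 12). The threshold is a chosen cut-off with no derivation, so there is no plan figure to reproduce. The documents give no expected AE or SAE rate, so every event total below is an assumption. The assumed unit is participants with at least one event, and the assumed test is two-sided Fisher exact. Arms of 50 and 25 stand for points part-way through accrual.

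**Step 1: does a pooled total settle the question?** Fix the total T and vary the split, at 100 per arm:

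| T of 200 | Even split | First split with p<0.01 |
|---|---|---|
| 8 | 4-4, p=1 | 8-0, p=0.0068 |
| 20 | 10-10, p=1 | 16-4, p=0.0081 (15-5 gives 0.032) |
| 40 | 20-20, p=1 | 28-12, p=0.0075 |
| 60 | 30-30, p=1 | 39-21, p=0.0084 |

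At 50 per arm, T=20 of 100 fits 10-10 (p=1) and 16-4 (p=0.0050). The same pooled table is compatible with the illustration being met and with no difference at all.

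**Step 2: when does the total alone rule the illustration out?** Only when even the most lopsided split stays at or above 0.01. With n per arm and all T events in one arm (T no larger than n), Fisher p = 2 × C(n,T) / C(2n,T), where C(a,b) is the number of ways of choosing b from a. For n=100:

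- T=7: 2 × C(100,7)/C(200,7) = 0.0140, so ruled out.
- T=8: 2 × C(100,8)/C(200,8) = 0.0068, so possible.

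The test treats events and non-events alike, so the same holds at the top of the range: 100 v 93 gives 0.0140 and 100 v 92 gives 0.0068. Checking every total at each size:

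| Per arm | Ruled out by the total alone |
|---|---|
| 100 | below 8 or above 192 of 200 |
| 50 | below 8 or above 92 of 100 |
| 25 | below 7 or above 43 of 50 |

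Between those limits the pooled table cannot answer.

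**Step 3: does the unstated test matter?** At 100 per arm, 9 v 1 gives 0.018 by Fisher and 0.009 by a pooled z test. At 50 per arm the values are 0.016 and 0.008. The two tests fall on opposite sides of 0.01.

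**Step 4: is an arm comparison assigned elsewhere?** The monthly reviews by the PIs and project managers (Sections 7.2, 7.6 and 10.3.5) and the review table in 10.3.5 do not mention arms. Section 12 has the PI, project managers, investigators and staff attend committee meetings and present the data, and describes no closed session. Section 6.2.3 keeps data managers and data analysts blind for all analyses. Section 6.2.2 gives the sequence to the biostatistician and the running of randomization to the project managers, but gives neither a safety comparison.

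**The case against.** **It is only an illustration.** The p<0.01 difference follows an e.g., and the committee decides on stopping rules. This stands: it is not a binding boundary. It is still the only number offered, and the tables described cannot inform it.

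**The governing documents are not supplied.** Section 7.6 defers to the Data and Safety Monitoring Plan and the committee charter. Either may already provide review by arm. This stands and limits the claim to the text supplied.

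**The committee has other routes.** This also stands. A reader might infer that the committee cannot detect harm or cannot act. The documents do not support that. Under the table in 10.3.5, unexpected and related SAEs reach it per occurrence, and AE rates and other SAEs reach it annually. Section 7.6 has patterns of concern reported to it as necessary. It can act on the pooled triggers in 9.4 and 11.4 and on the other grounds in Section 8. Section 7 lets it oversee analysis and "take whatever steps are necessary to protect the safety and well-being of human subjects", which would cover asking for arm data.

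**Someone could supply the arm codes.** A reader might infer that everyone who holds the allocation is described as blind. That goes too far. The blinding clause for analyses in 6.2.3 names data managers and data analysts, not the biostatistician. Section 9.6 lists project biostatisticians among those who analyse the data, so that role's status is unclear rather than stated. Project managers do appear in 6.2.3 among the follow-up collectors who stay blind, although 6.2.2 has them run randomization.

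**That a total does not fix its split is obvious.** True. The arithmetic only shows how narrow the range is in which a pooled table would be enough.

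**Conclusion.** The mismatch is real but narrow. On the text supplied, the protocol's only numerical illustration of a safety stop cannot be evaluated from the Study Report tables that Sections 7.6 and 12 prescribe, and no section assigns the comparison. With 100 per arm and Fisher's test on participants, this holds for every pooled total from 8 to 192 of 200. Because event rates are not given, the documents do not show how likely a relevant imbalance is, and no harm to participants or bias in the results is demonstrated. The conclusion rests on the supplied text alone and would fall away if the charter or monitoring plan provides arm-level safety review. It is worth fixing because it concerns participant safety and costs little.

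**What to change.** 1. Check the charter and the Data and Safety Monitoring Plan. If they provide arm-level safety review, cite it in Sections 7.6, 8 and 12. Nothing more is then needed on the arm comparison.
2. If they do not, reconcile Sections 7.6 and 12 with Section 8. Preferably keep the open pooled report and add a closed table of AE and SAE counts by coded arm, seen only by the committee, with the PIs and study staff excused. State the test and unit beside the p-value, for example two-sided Fisher exact on participants with at least one event.
3. Have that table prepared by an existing team member who holds the allocation and neither collects follow-up data nor runs the blinded analyses. The biostatistician is a candidate, but Sections 6.2.3 and 9.6 must first make clear whether that role stays blind.
4. Alternatively, reword the illustration so that it does not depend on comparing arms. The wording is for the sponsor and the committee.
5. Separately, make Sections 7.6 and 10.3.5 agree on who receives the Annual Report, and say whether its AE list is pooled.

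**Cost.** Wording in Sections 7.6, 8, 10.3.5 and 12, and in 6.2.3 and 9.6 if the closed table is chosen. The closed table adds one coded table per annual review (about four in a 4-year project) and one named unblinded preparer. Its downside is that arm-level safety data would exist within the committee. Rewording the illustration adds no further work.

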9. STATISTICAL CONSIDERATIONS

9.1 General Design Issues

To minimize the likelihood of Type I errors, analyses for testing the main study hypotheses will be planned a priori and will be limited to the examination of a set number of outcomes. In addition, analyses that are central to the purpose of the study will be clearly identified as confirmatory hypotheses and will be clearly identified as separate from exploratory analyses. Prior to hypothesis testing, data will be examined and described using standard univariate summary measures and bivariate statistical measures of association, as well as graphical displays of the distribution of responses on all variables. Statistical assumptions required for the methods of analysis outlined in this section will be rigorously tested. Distributions of measures such as intensity and frequency of

pain, counts of buprenorphine non-adherence over follow-up, pain related functioning scores, and frequency of substance use that have multiple items and/or have potentially non-linear distributions will specifically be examined graphically to understand their distribution. The failure of statistical assumptions necessary for the techniques planned will be addressed using: 1) a different method of analysis (e.g., using a different link function in generalized linear models that is appropriate to the data distribution, using non-parametric tests instead of parametric tests); or 2) the data will be appropriately transformed to a distribution that meets the assumptions of the proposed statistical test.

Many of the proposed analyses involve the examination of differences over follow-up between the participants of the PPMI and EUC groups. Every effort will be made to ensure balance between groups on key characteristics during randomizations, with checks on the randomization on an ongoing basis during the study.

To minimize missing data, we will make every effort to gather follow-up information for all participants. Specific strategies to retain participants that have proven successful in our prior research are described above. We have also chosen analytic methods that will maximize the number of participants who will be included in analysis. Nonetheless, if our examination of the pattern of ‘missingness’ suggests that our assumptions are unsuitable for the models, we will handle missing data via multiple imputation procedures as described by Schafer.

The primary goal for the RCT is to examine the efficacy of PPMI by testing differences between the PPMI and EUC conditions on primary and secondary outcomes over 3-months and 12-months of follow-up. The primary analyses will involve calculating the attrition rates up to the first 3-months of follow-up. The secondary analyses will involve up to the 12-month follow-up. We will also examine the impact of telehealth PPMI on pain level, pain-related functioning, and frequency of substance use, including prescription and non-prescription opioid use at these two time points. We will also quantify session attendance and note the percent of participants who did not complete all sessions to identify ways to decrease drop-out and non-compliance to the intervention.

9.2 Sample Size and Randomization

Sample size estimates were guided by our prior work on psychosocial interventions for pain during addiction treatment and prior trials that used MAT retention as an outcome and calculated using Stata. In studies of buprenorphine programs, retention varies widely but generally is around 50% in studies with at least 3-months of follow-up and robust sampling.²⁶ For a time-to-event analysis we assumed an event rate of 50% in EUC, where the event is dropping out of treatment, and based calculations on a two-sided $\alpha=0.05$. A hazard ratio of 0.5 (i.e., PPMI less likely to drop out of treatment) would achieve >85% power with a sample size of 200, or 100 per group. Given that we will be able to infer treatment retention even for participants who drop out of the study, our primary outcome analysis was based around our complete sample size of 200.

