Numerous efforts are underway to expand capacity to deliver MAT in the community. In 2017, [name], a colleague and close collaborator with Drs. [name] and [name] was awarded a grant from the state of Michigan through STR funds to develop the Michigan Opioid Collaborative (MOC), a multi-component program to increase the workforce of clinicians delivering MAT as well as referrals to these clinicians. The MOC uses a combination of care managers and addiction physician consultants to provide support to clinicians in the community to increase delivery of MAT. The MOC is established in four counties included within the Community Mental Health Partnership of Southeast Michigan (CMHPSM), which include rural, suburban, and metropolitan regions. However, even if this (and other similar projects underway throughout the United States) are successful in expanding treatment capacity so that patients can be identified and obtain MAT, poor treatment adherence remains a significant problem. Currently, rates of retention on MAT are close to 50% at 3 months on buprenorphine²⁴⁻²⁷ and discontinuation is associated with not only a higher prevalence of relapse to opioid use but also high mortality.^{31,35} Although there is some limited support for contingency management,^{36,37} there is very little support for other behavioral interventions to improve MAT treatment adherence.³⁸ Newer and improved techniques are needed to address poor treatment adherence in order to optimize the positive impact of MAT.

Pain as a driver of opioid use and poor treatment adherence in MAT. Pain is highly prevalent among individuals receiving MAT, with prevalence rates often greater than 50% in patients receiving MAT.^{4,5} When present, pain is associated with worse MAT outcomes including increased craving for substances and with increased illicit opioid use.³⁹⁻⁴¹ Many patients with OUDs view pain as a central part of the onset of initial OUD symptoms as well as the ongoing maintenance of opioid misuse.^{28,42-44} Although these findings may partially reflect recall bias, they also clearly capture the fact that those with active OUD view pain as a key driver of substance use. Similarly, maladaptive reactions to pain likely influence engagement in adaptive behaviors central to recovery from OUD, including MAT adherence.

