Planned enrollment rates for this phase of this project are based on current rates of opioid overdose deaths by race/ethnicity in Michigan, as well as the actual enrollment of our previous project with individuals with co-occurring pain and substance use disorders recruited from a residential treatment program in Michigan. The study sample is designed to be broadly representative of patients in Michigan who are being prescribed buprenorphine for the treatment of an OUD. All eligible participants receiving buprenorphine treatment at the recruitment sites will be approached for participation, regardless of gender or minority status. If we have an excess number of potential participants to approach at any given time during the recruitment window, we will prioritize recruitment of women and minorities whenever possible. For the Veteran sample, there was an average of approximately 270 patients diagnosed with OUD receiving buprenorphine at the Ann Arbor VA in 2018. With a one-year drop-out rate higher than 50%, an estimated 135 are new patients per year. We conservatively estimate that, out of both community and veteran participants, 50% of patients who complete the eligibility screen will have begun buprenorphine treatment within the past 6 months, 50% of those participants will have pain, 90% will meet criteria for an OUD within the past 12 months, and 80% will consent to the study (based on our prior work). This should be more than enough potential participants to make the proposed study feasible. However, if for some reason we have difficulty recruiting participants, we will expand recruitment to other nearby VA Medical Centers (e.g., Detroit VA is approximately 50 miles away) and/or we will expand our contact with additional MAT providers. Specific strategies will be used to identifying potential participants at each recruitment site. Due to the varied location and nature of the recruitment sites, several strategies may be applied at each site to ensure all potential participants are reached for recruitment. For additional details regarding recruitment strategies, please see Section 4.3 'Study Enrollment Procedures' below.

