4.1 Inclusion Criteria

Participant responses to study measures will be evaluated by research staff to ensure all eligibility criteria are met before participants are enrolled into the full RCT. Participants will complete a brief eligibility screening survey to ascertain appropriateness for the study. Any questions pertaining to participant responses will be clarified with the participant prior to the determination of eligibility status. The ability to understand study procedures and to comply with them for the entire length of the study will be assessed prior to enrollment in the trial.

Inclusion criteria for the main RCT trial are:

- (a) at least legal adult age to consent without a guardian ((18 years of age or older in all states except Alabama (requires 19 years of age), Nebraska (requires 19 years of age), and Mississippi (requires 21 years of age))
- (b) having a diagnosis of an OUD within the past 12 months;
- (c) started buprenorphine (*the term we use to refer to all buprenorphine products including buprenorphine/naloxone*) treatment within the past 6 months
- (d) at least moderate or greater self-reported pain on average over the past 3 months;
- (e) regular and consistent access to a telephone and willingness to use the phone for study telephone sessions.

Participants in this study will be of legal adult age to consent without a guardian (18 years old or older in most states unless in Alabama (requires 19 years of age), Nebraska (requires 19 years of age) and Mississippi (requires 21 years of age) for several reasons. All participants will be patients prescribed buprenorphine for the treatment of an OUD who also experience pain. Due to the differences in pain management and intervention strategies for those 17 and younger relative to older individuals, a separate study would be required to appropriately examine opioid safety among children and adolescents age 17 and under with pain. Individuals age 18 to 20 will be included in the study because individuals in this age range receive medical care services related to OUD and pain in the same manner as those individuals age 21 and older.

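### The >85% power in section 9.2 needs an EUC 3-month drop-out rate of about 47% or more, and the assumed 50% is not justified for patients already 0 to 6 months into treatment

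*Combined protocol and SAP*

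**What the plan says.** Section 9.2 sets up a time-to-event calculation in which the event is leaving buprenorphine treatment. The control-arm input is "we assumed an event rate of 50% in EUC". With a hazard ratio of 0.5 and a two-sided 5% level, the plan concludes that this "would achieve >85% power with a sample size of 200, or 100 per group".

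The 50% is supported in two places. Section 9.2 says that "retention varies widely but generally is around 50% in studies with at least 3-months of follow-up", without saying when the clock started in those studies. Section 2.1 says that "rates of retention on MAT are close to 50% at 3 months on buprenorphine", which reads as time since treatment began.

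The trial uses a different clock. Section 6.2.3 counts the primary outcome over 3 months after enrollment. Under section 4.1, entrants must have started "treatment within the past 6 months" and must have taken a dose in the 10 days before the enrollment interview. No section adjusts the 50% for this or gives a drop-out rate counted from enrollment.

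**The concern.** Someone who starts buprenorphine, stops and does not resume cannot be enrolled. Entrants are therefore those still on treatment at some point between 0 and 6 months. If the risk of stopping falls as treatment goes on, their next 3 months will contain fewer events than the first 3 months after starting.

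Separately, follow-up of 3 months or more may include studies in which the 50% built up over a longer period. In that case the 3-month rate would be lower even when counted from treatment start.

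Power for a Cox test depends on the number of events. If the control rate is below 50%, the trial has less power at its own planning effect than it states, and a null result could be read as evidence of no effect when it is not.

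**Working it through.** **Inputs.** Section 9.2 gives a hazard ratio (HR) of 0.5, two-sided alpha of 0.05, 100 per arm, an EUC event rate p of 50%, and no inflation for drop-out. It does not name the power formula; Schoenfeld's is used here.

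**Formulas.**
- PPMI event rate under proportional hazards: q = 1 − (1 − p)^0.5
- Expected events: d = 100p + 100q
- Power = Φ(√d × |ln 0.5| / 2 − 1.96)

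**Step 1: the plan's own figure.** q = 1 − 0.5^0.5 = 29.3%, so d = 50 + 29.3 = 79.3. √79.3 × 0.693 / 2 = 3.09, and 3.09 − 1.96 = 1.13, so power is 87.0%. The stated figure reproduces. Freedman's formula gives 84.3%, and a comparison of two proportions (50% against 29.3%) gives 85.5%.

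**Step 2: power at other control rates, HR and N unchanged.**

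| EUC 3-month rate | PPMI rate | Events | Power |
|---|---|---|---|
| 55% | 32.9% | 87.9 | 90% |
| 50% | 29.3% | 79.3 | 87% |
| 45% | 25.8% | 70.8 | 83% |
| 40% | 22.5% | 62.5 | 78% |
| 30% | 16.3% | 46.3 | 66% |
| 20% | 10.6% | 30.6 | 48% |

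A power of 85% needs about 75 events. That corresponds to an EUC rate of about 47.3%, so the margin below the planning value is under 3 percentage points.

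**Step 3: does late entry lower the rate?** The documents give no hazard shape, so this step illustrates how the answer depends on it. Assume a Weibull drop-out curve from treatment start with 50% out at 3 months: S(t) = exp(−λt^k), λ = ln 2 / 3^k. A patient entering at month e has a 3-month event probability of 1 − exp(−λ[(e + 3)^k − e^k]). The first result averages this evenly over e from 0 to 6; the second weights entry by who is still on treatment.

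| Assumed shape k | EUC rate, even / weighted | Power, even / weighted |
|---|---|---|
| 1.0 (constant hazard) | 50% / 50% | 87% / 87% |
| 0.8 | 40.9% / 42.0% | 79% / 80% |
| 0.6 | 31.6% / 33.1% | 68% / 70% |

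The loss depends entirely on whether and how fast the hazard falls. With a constant hazard, later entry costs nothing.

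**The case against.** The strongest reply is that the direction of any error is unknown.

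- Section 9.2 states no time origin. That the 50% runs from the first dose is an inference from section 2.1.
- Several features could push the rate up. The event is any first run of 7 days without buprenorphine (section 9.5.1), which is broader than leaving a program. People restarting after a lapse of at least 30 days count as new episodes, and one dose in the previous 10 days is enough for entry (section 4.1). Everyone has at least moderate pain, which section 2.1 treats as a possible cause of drop-out. At a 55% control rate, power is 90%.
- Rewording the power statement changes neither the sample size nor the test, and reporting the hazard ratio with its confidence interval already guards against misreading a null result.

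All of this stands as a limit on the conclusion. It does not supply the missing justification for 50%.

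Section 4 says that loss to follow-up may be counted as non-adherence. This adds events but does not rescue power if losses are equal in both arms. With the 20% loss that section 4 expects and a true EUC rate of 50%, the observed rates are 0.50 + 0.20 × 0.50 = 60% and 0.293 + 0.20 × 0.707 = 43.4%. The HR becomes ln(0.566) / ln(0.40) = 0.62 and power is 67.6%, despite 103 events.

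A reader might also infer from the one-year drop-out rate above 50% in section 4 that 50% at 3 months is possible only with a steeply falling hazard. The documents do not support that. The figure is an open-ended lower bound for one VA clinic, given to estimate recruitment. A constant hazard of 50% per 3 months implies 1 − 0.5^4 = 94% at one year, which also satisfies it.

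**Conclusion.** The calculation is correct at its own inputs, but the 50% control rate is not justified for the population and time origin of this trial. The claim of more than 85% power is therefore conditional, and the margin is thin: it fails once the EUC rate counted from enrollment is below about 47%. Power is 78% at 40% and 66% at 30%. These figures assume a true HR of 0.5, proportional hazards, equal arms, all 200 patients contributing, and Schoenfeld's formula.

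A reader might conclude that the trial is probably underpowered, or put one number on the loss by assuming a one-year drop-out rate. Neither step is supported. Both need a falling hazard, which no section documents, and a longer-term drop-out figure for this population, which the documents do not give. What is established is a missing justification to which the stated power is sensitive, not a demonstrated shortfall.

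**What to change.** **Section 9.2.** Either justify 50% as a 3-month rate counted from enrollment in patients 0 to 6 months into treatment, or state that power above 85% requires an EUC rate of about 47% or more and give power across control rates of 20% to 55%, as in the second step of the working.

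**Section 9.6.** Prespecify time since the start of the current buprenorphine episode as a covariate in the primary Cox model, with its form fixed in advance (for example, months as a continuous term). For people who restarted, count from the restart, in line with the new-episode rule in section 4.1. Sections 6.2.1 and 6.2.2 already require the start date of the most recent episode to be confirmed before enrollment. Time on treatment is plausibly prognostic, is not a stratification factor (section 9.2.1), and is not named in the Cox model. The text should say that the covariate does not replace missing events and that any gain in power is likely small.

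**Cost.** A short change of wording and one covariate. No extra patients, visits or data are needed. The power statement becomes less favorable. Both changes should be settled before outcomes are examined by arm.
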